## 2. BACKGROUND AND SIGNIFICANCE

In 2008, approximately 69,000 patients were diagnosed with urinary bladder cancer and 14,000 patients were expected to die from bladder cancer. Radical cystectomy with pelvic lymphadenectomy and urinary diversion is the standard of care for high grade carcinoma *in situ*, high grade recurrent superficial bladder cancer, or tumor invading the muscularis propria. Radical cystectomy with pelvic lymphadenectomy is associated with adequate survival outcomes and compares favorably with other treatment modalities. However, this operation is an extremely complex and involved surgical procedure associated with considerable postoperative morbidity.

Traditionally, an incision is made from just above or at the level of umbilicus to the pubic symphysis. The bladder, prostate gland, and surrounding lymph nodes are removed followed by urinary diversion which consists of connecting the urinary tract into a segment of intestine. The reported major and minor complication rates after open radical cystectomy are approximately 13% and 67%. More recently, less invasive surgical treatments with robot-assisted laparoscopy have been advocated. Robot Assisted Radical Cystectomy (RARC) is one such approach where the radical cystectomy and pelvic lymph node dissection are accomplished by a robot assisted laparoscopic approach. After the completion of the cystectomy and the lymph node dissection, a small periumbilical or infra-umbilical midline incision is made to complete the urinary diversion.

In other surgical procedures, such as nephrectomy, minimally invasive approaches have been associated with less blood loss, shorter hospital stay, less use of pain medication and faster return to preoperative levels of independence. One would expect that RARC might offer similar advantages over open cystectomy. Furthermore, there is evidence that efforts to compensate for the insensible losses and blood loss associated with open surgery may contribute to the high complication rate. Therefore, there is reason to expect that RARC might reduce complication rates compared to open cystectomy.

However, RARC is being marketed as superior to the traditional open operation without systematic comparative evaluations through randomized trials. The purported advantages of RARC from small-volume, single-institution series are decreased blood loss, decreased blood transfusion rates, decreased pain and opioid requirement, earlier time to oral intake, decreased hospital stay, fewer wound complications, and expedited perioperative and postoperative convalescence and recovery. Additionally, there does not appear to be any compromise in the oncologic outcome as determined by pathology of surgical margins and number of pelvic lymph nodes removed. However, despite these advantages, little is known regarding recovery to preoperative

functional independence with RARC. Also, RARC is associated with a steep learning curve as well as significant cost enhancements. All outcome studies of RARC are either case series reports or comparative studies with major methodological limitations. Additionally, all are limited by major selection biases such as patients with more favorable oncologic, demographic, and clinical characteristics undergoing the RARC compared to the open approach. Thus the perception that patient having RARC may have a better recovery is potentially due to the bias of preferential patient selection. Lastly, comparisons of open and RARC should be cautiously interpreted since they have been performed by a variety of surgeons with different training and experience levels.

To date, no study has evaluated the outcomes measuring postoperative recovery using objective parameters of functional independence in patients undergoing RARC nor specifically compared it to outcomes following open cystectomy. Studies evaluating short-term Quality-of-Life (QOL) outcome measures following open cystectomy have not been performed yet. Lawrence et al. conducted a prospective cohort study to systematically describe the clinical course and predictors of long-term recovery to preoperative levels of functional independence in patients after major elective abdominal operations, using both self-report and performance-based instrument. They found that a number of clinical factors independently predicted optimal functional recovery. Serious postoperative complications were consistent independent predictors of poorer recovery and longer time to recovery. Poor preoperative physical performance status (ECOG scale), serum creatinine > 1.5 mg/dL and albumin < 3 mg/dL independently predicted poor recovery at 6 months. However, to our knowledge, no one has tested the hypothesis that utilization of the robotic technique would independently improve recovery and result in superior short or long-term QOL outcomes.

### **3. OBJECTIVES AND SPECIFIC AIMS**

#### **Primary End Points**

##### Specific Aim 1 :

1. Two year progression free survival.

##### Specific Aim 2 :

1. Serum Hemoglobin, Serum Creatinine and Serum Albumin levels at baseline and in the post operative period at 4-6 weeks, 3 months, 6 months, 12 months, 24 months, and 36 months.
2. Quality of Life (QOL) outcomes at baseline and in the post operative period at 3 months and 6 months using the Functional Assessment of Cancer Therapy - Vanderbilt Cystectomy Index (FACT-VCI) as well as the Short Form 8 (SF-8) Questionnaires.

3. Compare surrogates of surgical quality by evaluating surgical margin status and number of lymph nodes harvested.
4. Compare surgical morbidity by evaluating complication rates at 90 days post operative using the modified Clavien grading system.
5. Perioperative measures such as Estimated Blood Loss (EBL), Blood transfusion rates, total intraoperative fluid requirements, total operative time, total postoperative length of hospital stay and analgesic requirement.
6. *3 year progression free survival in 65% of patients.*

Specific Aim 3 :

**A. Patient Reported Measures of Functional Independence**

1. Activities of Daily Living (ADL) scores at baseline and in the post operative period at 4-6 weeks, 3 months, and 6 months.
2. Instrumental Activities of Daily Living (IADL) scores at baseline and in the post operative period at 4-6 weeks, 3 months, and 6 months.

**B. Performance Related Measures of Functional Independence**

1. Hand Grip Strength Test outcomes at baseline and in the post operative period 4-6 weeks, 3 months, and 6 months.
2. Timed Up and Go Walking Test outcomes at baseline and in the post operative period 4-6 weeks, 3 months, and 6 months.

**Secondary End Points:**

1. Compare fixed and variable costs associated with RARC and ORC operating room and hospital component.

**4. EXPERIMENTAL DESIGN**

This multi-institutional, randomized trial will enroll approximately 350 participants with approximately 175 participants in each arm of the trial at approximately 15 participating institutions. This study aims to determine whether Robotic-Assisted Radical Cystectomy (RARC) for treatment of bladder cancer provides a non inferior oncologic control compared to traditional Open Radical Cystectomy (ORC), as measured by two-year progression-free survival. We propose a multi-institutional approach where participants randomized to both groups will have their surgery performed by experienced surgeons to eliminate institutional and surgeon bias.

## **Inclusion/Exclusion Criteria**

### Subject Inclusion Criteria:

1. Patient must have biopsy proven bladder cancer. Official pathology report reviewed at the participating institution is required.
2. Bladder cancer must be clinical stage T1-T4, N0-1, M0. (AJCC 7th edition) or refractory cis (carcinoma in situ).

### Subject Exclusion Criteria:

1. Inability to give informed consent.
2. Prior major abdominal and pelvic open surgical procedures that would preclude a safe robotic approach, as determined by the treating surgeon.
3. At the discretion of the treating surgeon, any pre-existing condition such as severe chronic obstructive pulmonary disease that precludes a safe initiation or maintenance of pneumoperitoneum over a prolonged period of time and during surgery.
4. Age <18 or >99 years.
5. Pregnancy.

## **Recruitment and Consent Procedures**

Patients who meet the eligibility criteria will be approached by research staff to determine whether they are willing to participate in the study. To eliminate selection bias, any patient who is determined to be a candidate for RARC will be given an option to participate in the study. The inclusion of patients eligible for this study will in no way compromise the quality of health care they will receive. Prior to study entry, the study staff will explain to each potential subject the research objectives, risks and benefits of study participation, alternative treatments available, and the subjects' rights and responsibilities. If the patient agrees to participate, informed consent will be obtained and, after consenting, randomization will take place. Participation in this study will last up to approximately 5 years.

## **Research Procedures**

### Randomization

**Eligible, consented patients must be enrolled (i.e., randomized) no more than 60 days prior to surgery.** This study uses a web-based patient enrollment and randomization system, through the data management services of Cancer Research And Biostatistics (CRAB). The patient enrollment/randomization eCRF (electronic Case Report Form) is accessed online through the study website at <https://prodq.crab.org/[name]/Login.aspx>. Access is protected and available to authorized users only. To request access to this system, or for questions or assistance using the website, please contact: [[contact]](mailto:[contact]) – please specify “[name] Robotic Surgery” in the email subject line.

### Nodal templates (equivalent for robotic and open procedures)

Minimum LND (men and women) – all potential lymph node bearing tissue with the lateral limit the genitofemoral nerve, distally Cooper's ligament to include the lymph node of Cloquet, proximally the crossing of the ureter over the common iliac vessels, medially the bladder to include the tissue medial to the hypogastric artery, posteriorly the floor of the obturator fossa with circumferential mobilization of the external iliac artery and vein.

### Submission and processing of specimens

The cystectomy specimen (with or without uterus, ovaries, or vaginal cuff in females and prostate in males) will be submitted en bloc, processed and assessed in a standardized fashion at all the participating institutions for margin status along with histology, size, stage, grade and presence/absence of lymphovascular invasion. At a minimum the LND will be submitted in two separate packets labeled left and right pelvic. All of these regions may be submitted in smaller packets (e.g. external iliac, obturator, internal iliac) at the surgeons preference. The standardized Cystectomy Pathology Form will be submitted to CRAB.

The perioperative care measures will be performed per institutional standard based on each institution's policy.

**Progression free survival:** From the date of surgery to the date of first documentation of progression or death due to any cause. Patients last known to be alive and progression-free are censored at the date of last contact. Progression will be determined using RECIST 1.1 criteria by the treating physician based on radiographic or pathologic evidence of disease progression, or death from disease. Any documented recurrence will be considered progression. All patients will have been followed for at least 2 years and 65% of patients will have been followed for 3 years.

**Overall survival:** From date of surgery to date of death due to any cause. Patients last known to be alive are censored at the date of last contact.

Serum hemoglobin and a comprehensive metabolic panel (CMP) will be measured on 10 cc of blood obtained by a venipuncture. These laboratory parameters are part of a routine preoperative work up and postoperative follow up in patients undergoing radical cystectomy and urinary diversion. No extra laboratory tests will be administered to the subjects enrolled in this trial.

Pathologic data will be obtained from the pathology reports after surgery with particular emphasis on the involvement of surgical margins with cancer, total number of lymph nodes harvested and their involvement with cancer as well as the pathologic stage of the tumor. All institutions will adopt a standardized procedure to process the cystectomy specimens along with the lymph nodes. A standardized form will be used to collect all the information pertaining to specimen processing and staging by the participating institutions. A copy of the pathologic form will be available in the patients' clinical records.

Perioperative mortality and morbidity will be evaluated using the modified Clavien grading system for complications by prospectively recording the intraoperative and post operative complications until discharge and by patient interview during post discharge period until 4-6 weeks after surgery. The above data will be separately recorded in the patient's clinical records in an inpatient and outpatient setting.

Perioperative measures such as estimated blood loss (EBL), blood transfusion rates, total intraoperative fluid requirements, total operative time, total postoperative length of hospital stay and analgesic requirement will be prospectively recorded during the surgery and the postoperative hospital stay using the anesthesia, operative, nursing and inpatient medical records by a research coordinator. All medications will be converted to morphine equivalents by using the online calculator The Clinician's Ultimate Reference found at <http://www.globalrph.com/narcoticonv.htm>

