### Power and Significance

The margin for this study is 15% which means that RARC would be considered inferior if the true progression free survival at two years was more than 15% lower than the progression-free survival at two years in the ORC arm. A total of 288 evaluable patients (144 patients per arm) yield a study with 80% power and a two-sided significance level, alpha, of 5% to correctly reject the null-hypothesis of unacceptable inferiority. These calculations are based on the assumption that progression-free survival at two years in the patients receiving ORC is approximately 71% and that the rate of progressions at two years is binomially distributed. Evaluable patients are defined as eligible patients who have no major protocol deviations and have 90-day post-surgery follow-up data. Major protocol deviations will be recorded for patients with no surgery given, where surgery was started correctly but discontinued before cystectomy was completed; or where the patient received a surgery type different from their randomization assignment for any reason. In addition, a major protocol deviation will be recorded if the surgery begins as assigned, but the robotic procedure is aborted and an open procedure is required to complete the operation.

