### **Accrual and Study Duration**

We anticipate participation of 15 sites and an accrual of approximately 110 eligible patients per year. Assuming a maximum drop-out rate of 10%, a total of approximately 350 patients (approximately 175 patients in each arm) will be accrued to this study. Thus approximately 350 patients will be accrued in approximately three years. All patients will be followed for at least two years for progression. Based on the accrual estimates, after three years of accrual and two additional years of follow-up, 65% of patients will have follow up available to evaluate progression free survival at 3 years. Thus the study duration is expected to be approximately five years.

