### **Analysis of Primary Endpoint**

A one-sided mantel-Haenszel test with half the alpha (0.025) will be used for testing the primary non-inferiority hypothesis that compares progression free survival at two years in the two treatment arms.

In superiority trials the intent to treat (ITT) population is widely accepted as the analysis population for the primary endpoint as it gives the most conservative result of such a study. In contrast, for non-inferiority trials the inclusion of ineligible or untreated patients or the lack of adherence to the assigned treatment is expected to increase the noise of the study and make the two treatment arms look more alike, thus the overall results of the study less conservative. Thus we will use the per-protocol (PP) population as the analysis population for the primary endpoint. We will also perform a sensitivity analysis of the primary endpoint using the ITT population. These two analysis populations are defined below. The design and analysis of this trial are based on the SWOG standards for noninferiority trials, which are detailed the chapter 12 in the Handbook for Statistics in Clinical Oncology, second edition, Chapman & Hall 2006.

Serum hemoglobin, serum creatinine and serum albumin levels will be taken at baseline and at a variety of time points post-surgery throughout the study. Linear mixed effects will be used to compare these blood levels and their changes over time between the two treatment groups.

QOL outcomes will be measured at baseline and in the post-operative period at 3 and 6 months using the Functional Assessment of Cancer Therapy – Vanderbilt Cystectomy Index (FACT-VCI) as well as the Short Form 8 (SF-8) Questionnaires. Simple descriptive statistics, such as mean and standard deviation, will be used to summarize the FACT-VCI and the SF-8 scores at each time point and for each treatment group. A multivariate linear mixed effects model will then be fitted to each score in this repeated measures design. The main effect will be visit (at baseline, 3 and 6 months) and will be treated as a categorical variable to accommodate for the non-linear trends. If the exact time corresponding to a particular visit differs significantly between patients a variable

representing the deviation from the visit-specific mean time will be added to the model. Standard diagnostic tools will be used to assess model fit.

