### **Analysis Populations:**

#### **Per Protocol Population (PP Population):**

The per-protocol population includes all patients who have met inclusion/exclusion criteria and received the surgery to which they were randomized. This is the primary efficacy population. All efficacy and QL endpoints will be assessed using this population.

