## **Intent-to-Treat Population (ITT Population):**

The ITT population includes all patients who have been randomized to the trial. Patients are assigned to treatment arms based on what they are “randomized” to receive. This is the sensitivity analysis population of the primary efficacy endpoint.

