### **Subject Completion and Withdrawal**

A subject will be considered completed when he/she has completed all follow-up visits up to the 24 month evaluation. A subject may discontinue participation in this study at any time at the investigator's discretion or at the request of the subject. The reason for study withdrawal will be documented in the study related source documentation.

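### The ITT sensitivity analysis of 2-year PFS covers every randomized patient, but PFS is defined only from surgery, so patients never operated on have no time zero

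*Combined protocol and SAP*

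**What the plan says.** - **Endpoint.** The PFS definition in Section 4 (under Submission and processing of specimens) runs "From the date of surgery to the date of first documentation of progression or death due to any cause". Patients alive and progression-free are censored at last contact. No other PFS origin appears in the document.
- **ITT analysis.** Section 5, Analysis of Primary Endpoint: "We will also perform a sensitivity analysis of the primary endpoint using the ITT population". Section 5, Analysis Populations: "The ITT population includes all patients who have been randomized to the trial".
- **Primary analysis.** This uses the PP population: "The per-protocol population includes all patients who have met inclusion/exclusion criteria and received the surgery to which they were randomized". The other efficacy endpoints are also assigned to PP.
- **Gap before surgery.** Section 4 (Randomization; Treatment/Intervention Plan) allows up to 60 days from randomization to surgery.
- **Patients without surgery.** Section 5, Power and Significance: "Major protocol deviations will be recorded for patients with no surgery given". The same paragraph lists surgery stopped before cystectomy was complete, surgery of the other type, and robotic-to-open conversion.
- **Related records.** Section 6 says: "The reason for study withdrawal will be documented in the study related source documentation". Section 5 gives an overall allowance: "Assuming a maximum drop-out rate of 10%, a total of approximately 350 patients".

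**The concern.** The endpoint needs a surgery date and the ITT population does not. A randomized patient who never has surgery belongs to the ITT population but has no start date from which two years can be counted. Progression or death during the wait comes before the clock starts, and the plan has no rule for it.

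ITT is the only planned efficacy analysis that brings back patients excluded after randomization. Deviation and withdrawal records would show how many were never operated on. Their effect on the PFS comparison shows only if the ITT analysis counts them. The analyst must otherwise choose between leaving them out, scoring them as events, and scoring them event-free when no progression is documented, possibly with the data in view.

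**Working it through.** **1. The plan's own figure.** Inputs from Power and Significance: 71% in both arms, margin 15 points, one-sided 0.025, 80% power.
n per arm = 2 × 0.71 × 0.29 × (1.960 + 0.842)² / 0.15² = 143.7, so 144 per arm and 288 in total. At 144 per arm, SE = √(2 × 0.71 × 0.29/144) = 0.0535 and power = Φ(0.15/0.0535 − 1.96) = 80%. The stated figure reproduces. It rests on evaluable patients, who have all had surgery, so this point does not alter it.

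**2. Who lacks a time zero.** Of the four major deviations, only the absence of surgery leaves no surgery date. Stopped surgery, surgery of the other type and conversion each have one, so ITT can restore those patients as written.

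**3. Size in the ITT analysis.** The documents give no never-operated count. The nearest figures are ceilings covering other reasons too: 10% of 350 = 35 drop-outs, and 350 − 288 = 62 non-evaluable. Assumptions: 175 per arm, true PFS 71% in operated patients of both arms, k never operated in an arm, and q their assigned or true 2-year PFS.

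- Arm PFS = [(175 − k) × 0.71 + k × q] / 175
- Chance of meeting the margin = Φ((0.15 + RARC − ORC)/SE − 1.96), unpooled SE, unstratified

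Example, 9 RARC v 0 ORC, all events: RARC = 166 × 0.71/175 = 0.6735; difference = −3.65 points; SE = √(0.6735 × 0.3265/175 + 0.71 × 0.29/175) = 0.0493; chance = Φ(0.1135/0.0493 − 1.96) = 63%.

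Each cell gives the shift in points and the chance of meeting the margin. The value q = 35.5% is half of 71%.

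| Never operated, RARC v ORC | Left out | All events (q = 0) | q = 35.5% | All event-free (q = 1) |
|---|---|---|---|---|
| 9 v 0 | 0; 86% | −3.7; 63% | −1.8; 77% | +1.5; 93% |
| 5 v 2 | 0; 86% | −1.2; 80% | −0.6; 84% | +0.5; 90% |
| 9 v 9 | 0; 85% | 0; 85% | 0; 86% | 0; 88% |
| 0 v 9 | 0; 86% | +3.7; 97% | +1.8; 93% | −1.5; 80% |

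The expected lower bound at 9 v 0, all events, is −3.65 − 1.96 × 4.93 = −13.3 points, still inside the margin. It reaches the margin only at 13 v 0, all events: −5.27 − 1.96 × 4.96 = −15.0.

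**4. Equal losses with a true deficit.** Take 56% v 71% in operated patients and 9 v 9 never operated with a common q. The deficit becomes 15 × 166/175 = 14.2 points. With q = 35.5%, SE = 0.0513 and the chance of wrongly meeting the margin is Φ((0.15 − 0.1423)/0.0513 − 1.96) = 3.5%, against 2.5% if they are left out. The other values of q also give about 3.5%.

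**5. Edge case in PP.** A patient who progresses while waiting and then has the assigned operation meets the PP definition, with an event before time zero. Each such patient moves one arm's 2-year PFS by at most 1/144 = 0.7 points.

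**The case against.** The strongest reply is that little depends on this. The primary analysis is PP, no passage makes the non-inferiority conclusion conditional on ITT, and the imbalances above are hypothetical. That stands, and it keeps the point minor.

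A second reply is that the endpoint is PFS status at two years, treated as binomial, so an analyst could simply score a death before surgery as a failure. The analyst could, but two years still needs a start date, the only one given is surgery, and the plan does not state that scoring. Censoring at last contact does not help, because the duration still runs from surgery.

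A third is the reference to an outside standard: "The design and analysis of this trial are based on the SWOG standards for noninferiority trials". The cited handbook chapter may contain a rule. It cannot be checked here, and the plan does not state one.

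The PP edge case is thin. Table 1 schedules no imaging or disease assessment between baseline and surgery, so scheduled visits would rarely document such progression, and no frequency can be given.

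Three stronger readings are tempting and not supported:
- **That the plan says events before surgery do not count.** It does not. This follows from applying the definition literally.
- **That the primary result is compromised.** Never-operated patients are outside PP, and its sample size and power are unchanged.
- **That equal losses are harmless.** This is nearly so only when true PFS is equal. With a true deficit, restoring equal numbers dilutes it. That dilution belongs to ITT itself, and the plan gives it as the reason for making PP primary. A start-date rule will not remove it.

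**Conclusion.** Wrong as written, minor, and essentially confined to the ITT sensitivity analysis. With PFS dated only from surgery, that analysis cannot include all randomized patients: those never operated on have no time zero, and events before surgery fall ahead of it. Patients with the other listed deviations are not affected.

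The size depends on an unknown count and on its imbalance between arms. At the illustrative 9 v 0, the unstated scoring rule alone moves the chance of meeting the margin between 63% and 93%; at 5 v 2 the range is 80% to 90%. These figures assume 175 per arm, 71% PFS in operated patients and an unstratified test. They show how sensitive the ITT result is to the missing rule, and they do not predict what will happen in this trial.

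**What to change.** For the ITT analysis:
- start PFS at randomization;
- count progression or death before surgery as events;
- keep never-operated patients in their assigned arm;
- score 2-year status at the planned 24-month disease assessment for operated patients, and at 24 months from randomization for those never operated on.

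Report never-operated counts and reasons by arm. Keep the surgery-dated definition for the PP primary analysis, and add that progression documented before the assigned surgery counts as an event if the patient is in PP.

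**Cost.** Sample size and the PP test do not change. Follow-up forms are dated from surgery, so never-operated patients need a visit anchor from randomization. The ITT and PP clocks will differ by up to 60 days, so an operated patient's 24-month assessment can fall as late as 24 + 60/30.44 = 26.0 months after randomization. Under a constant hazard, two extra months would lower PFS from 71.0% to 0.71^(26/24) = 69.0%, similarly in both arms if waiting times are similar. Extending the ITT window to month 26 for everyone is not advisable, because a patient operated on early completes the study at the 24-month evaluation and may have no status that late. A second PP analysis on the randomization clock would separate the change of origin from the restored patients, but it is optional.
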